10.2 Procedures

NON-SERIOUS ADVERSE EVENTS

Non-serious adverse events must be recorded using medical terminology in the source document and in the case report form if they have a possible, probable or very likely suspect association to the study drug.

SERIOUS ADVERSE EVENTS

All adverse events meeting the definition of serious, regardless of severity or presumed relationship, must be recorded using medical terminology in the source document and in the case report form. Only SAEs that are “possibly”, “probably” or “very likely” related to the study drug must be reported using the Sponsor Serious Adverse Event Form within 24 hours of knowledge of the event. Exceptions to this include:

- Death, regardless of the cause, is considered a reportable SAE;
- Malignancy (except Basal Cell or Squamous Cell Carcinomas), regardless of causality, is considered a reportable SAE.

Whenever possible, diagnoses should be given when signs and symptoms are due to a common etiology (e.g. cough, runny nose, sneezing, sore throat, and head congestion should be reported as “upper respiratory infection”). Investigators must record in the CRF their opinion concerning the relationship of the SAE to study therapy. All measures required for serious adverse event management must be recorded in the source document.

OZ1: Clinical Protocol OZ1-HV1-202 Amendment 4; 07 June 2017

Subjects (or their designees, if appropriate) must be provided with a “study card” indicating the name of the investigational product, the study number, the investigator’s name, and a 24-hour emergency contact number.

All reportable SAEs occurring during the study period must be reported to the appropriate sponsor contact person by investigational staff within 24 hours of their knowledge of the event. If the SAE is a death or a life threatening event the Investigator must notify the Sponsor immediately by both telephone and FAX.

Information regarding serious adverse events will be transmitted to the sponsor using the Sponsor Serious Adverse Event Form, which must be signed by a member of the investigational staff. The initial report of a serious adverse event may be made by facsimile (fax) or telephone. It is preferable that serious adverse events be reported via fax. Subsequent to a telephone report of a serious adverse event, a Serious Adverse Event Form must be completed by the investigational staff and transmitted to the sponsor within 24 hours.

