---------------------------------------	-----------------	--	--

		
are consistent with those for HIV-infected patients on ART. Replication competent retrovirus (RCR) polymerase chain reaction (PCR) assay of patient samples showed no detectable RCR.
 
Phase I CD34+ Cell Study
 
This Phase I study was conducted at the University of California Los Angeles (UCLA), California, USA, in 10 patients, using autologous CD34+ cells collected from HIV-1 infected patients. Patients were not myeloablated. Following G-CSF mobilization and apheresis, the CD34+ cells were purified using a CD34+ specific antibody. The CD34+ cells were then introduced into culture with the growth factors Stem Cell Factor (SCF) and Megakaryocyte Growth and Development Factor. Approximately half the cells were transduced with LNL6 and half with OZ1. Both batches of cells were mixed and re-infused. Table 2 presents the purity, total number CD34+ infused (number/kg body weight), percent transduction and number of transduced (LNL6 + OZ1) cells. The first three patients treated received between 0.4%-4% mixture of LNL6- and OZ1-transduced cells. A modification to the transduction procedure was introduced, and retronectin (RN – a recombinant cell adhesion protein) was used to enhance transduction efficiency. The remaining seven patients received cells with transduction efficiencies ranging between 7 - 57 %.
 
(Table 2 inserted)
 
Patients were recruited over the period February 1998 to January 2000. The last three patients were enrolled substantially later (November 1999 to January 2000) than the first seven (February 1998 to October 1998). The time period since infusion for all ten patients ranges from approximately 4 to 6 years. Six patients completed the 3-year study period and 8 patients are participating in long-term follow up. Results to date show gene marking in bone marrow and peripheral blood mononuclear cells, specifically, purified T-cells, monocytes and granulocytes, and in purified naïve and memory CD4+ and CD8+ cells (Amado et al., 2004). The presence of gene marked cells with the naïve phenotype (CD45RA+/CD62L+) is direct evidence for the production of mature T-cells from the infused CD34+ cells (Amado et al., 2004, Tough et al., 1995; Aguila et al., 1997; McFarland et al., 2000). Thus, the transduced CD34+ cells have contributed to relevant hematopoietic lineages.
	
--	--	---	--

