--	---	--

	
PBMC samples (PCR). Archival storage of plasma and PBMC samples. PBMC archive for PCR analysis for the presence of Replication-Competent Retrovirus (RCR) using primers specific for amphotropic env retroviral gene sequences. Both PBMC cell pellets and cryopreserved cells are required for archive. Recording of SAEs Year 5+ Annual Visits Annual visits will include all assessments listed in the 2-5 year annual visits above. If the full blood count/differential and clonality of OZ1 integration in PBMC show no significant abnormality during the first 15 years post-infusion for patients receiving OZ1, these tests will no longer be performed for the remaining Long Term Follow-up Protocol. It is currently required that all other assessments continue for the lifetime of the patient.
	
OZ1 DNA is detected. Recording of adverse events (AEs). Annual Visits Year 5-15 post infusion Clinical History and Physical Examination including a detailed record of: -exposure to possible mutagenic agents eg radiotherapy or chemotherapeutic agents -new malignancies -new or exacerbated preexisting neurologic, autoimmune and hematologic disorders. Complete Blood Count (CBC), differential and platelet count. Archival storage of plasma and PBMC samples for Replication-Competent Retrovirus (RCR) and other safety testing as required Testing for clonality of OZ1/LNL6 integration in PBMC samples (PCR) including gene marking (quantitative OZ1 DNA-PCR). Quantitative analysis of PBMC sample for OZ1 RNA (RT PCR) if OZ1 DNA is detected. Recording of adverse events (AEs). Annual Visits Year 15+ post infusion Clinical History and Physical Examination including a detailed record of: -exposure to possible mutagenic agents eg radiotherapy or chemotherapeutic agents -new malignancies -new or exacerbated preexisting neurologic, autoimmune and hematologic disorders. Archival storage of plasma and PBMC samples for Replication-Competent Retrovirus (RCR) and other safety testing as required Recording of adverse events (AEs). If the full blood count/differential and platelet count and the clonality of OZ1 integration in PBMC show no significant abnormality during the first 15 years post-infusion these tests will no longer be performed for the remaining Long Term Follow-up Protocol. It is currently required that all other assessments continue for the lifetime of the patient. Unscheduled Assessments In addition to the annual follow up visit, unscheduled procedures may be performed in the event of an adverse event.
	

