9.1 Efficacy Evaluation	
There will be ongoing assessment of quantitative marking and expression of the gene transfer product in PBMC
	
Ongoing analysis of quantitative marking of the gene transfer product (OZ1 and LNL6) in peripheral blood mononuclear cells will be performed as part of the testing of OZ1 or LNL6 vector integration sites. This data will be used to independently assess changes in the number of peripheral blood mononuclear cells that carry the gene transfer product over time. Patients will have the option of consenting to the collection of additional blood samples for the ongoing assessment of OZ1 expression (OZ1 RNA- RTPCR).
	
To clarify the use of the data obtained from this analysis.

9.2 Safety Evaluations	
Serious Adverse Event data will be assigned a body system and preferred term using the MedDRA coding dictionary, Version 6.0. All Serious Adverse Events (SAEs) will be
	
Serious Adverse Event data will be assigned a body system and preferred term using the current MedDRA coding dictionary. All Serious Adverse Events (SAEs) will be recorded with respect to severity as per the ACTG 285 Toxicity Table (See Appendix 1).
	
The current version of the MedDRA dictionary will be used. Description of safety

	
recorded with respect to severity as per the ACTG 285 Toxicity Table (See Appendix 1). Serious Adverse Events will be summarized either in a tabular form, or via data listings. Data will be summarized annually for regulatory reporting.
	
Serious Adverse Events will be summarized either in a tabular form, or via data listings. Data will be summarized annually for regulatory reporting.
	
evaluations expanded to include all clinical observations.

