
10. ADVERSE EVENT REPORTING
 
10.2 PROCEDURES ADVERSE EVENTS
	
Only Serious Adverse Events (SAEs) that are “possibly”, “probably” or “very likely” related to the study drug that occur from two years after infusion will be reported on a SAE form by the Investigator. Death or malignancies (except Basal Cell or Squamous Cell Carcinomas) should be reported, regardless of causality assessment. All other SAEs (unrelated to the drug) will be recorded in the CRF as a summary of the event. SAEs may be reported by the patient to the site at the follow up visits or via spontaneous reporting between follow up visits.
 
For each serious adverse event reported, the investigational staff should obtain all the information required to complete the Serious Adverse Event Form (if applicable), in accordance with the guidelines. All measures required for serious adverse event management must be recorded in the source document and reported according to Sponsor instructions.
 
All reportable serious adverse events must be reported to the appropriate Sponsor contact person by investigational staff within 24 hours of their knowledge of the event.
 
If the SAE is a death or a life threatening event the Investigator must notify the Sponsor immediately by both telephone and FAX. The completed SAE form must be transmitted by FAX to JJR within 24 hours of knowledge of the event. The Investigator must provide the following minimal information: Protocol number, patient’s initials and date of birth, patient number or medication code number, date of treatment, nature of the adverse event and Investigator’s attribution.
 
All serious adverse events must be followed until any of the following occurs:
 
 the event resolves; the event stabilizes; the event returns to baseline, if a baseline value is 	
Non-Serious Adverse Events
 
Non-serious adverse events must be recorded using medical terminology in the source document and in the case report form if they have a possible, probable or very likely suspect association to the study drug.
 
Serious Adverse Events
 
All adverse events meeting the definition of serious, regardless of severity or presumed relationship, must be recorded using medical terminology in the source document and in the case report form. Only SAEs that are “possibly”, “probably” or “very likely” related to the study drug must be reported using the Sponsor Serious Adverse Event Form within 24 hours of knowledge of the event. Exceptions to this include:
 
Death, regardless of the cause, is considered a reportable SAE;
 
Malignancy (except Basal Cell or Squamous Cell Carcinomas), regardless of causality, is considered a reportable SAE.
 
Whenever possible, diagnoses should be given when signs and symptoms are due to a common etiology (e.g., cough, runny nose, sneezing, sore throat, and head congestion should be reported as “upper respiratory infection”).
 
Investigators must record in the CRF their opinion concerning the relationship of the SAE to study therapy. All measures required for serious adverse event management must be recorded in the source document.
 
Subjects (or their designees, if appropriate) must be provided with a “study card” indicating the name of the investigational product, the study number, the investigator’s name, and a 24-hour emergency contact number.
 
All reportable SAEs occurring during the study period must be reported to the appropriate sponsor contact person by investigational staff within 24 hours of their knowledge of the event. If the SAE is a death or a life threatening event the Investigator must notify the Sponsor immediately by both telephone and FAX.
	
Change to reflect updates to company safety reporting requirements clarify reporting requirements and expand safety reporting requirements to include non-serious, associated adverse events.

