## 1. INTRODUCTION

### 1.1. RESPONSIBILITIES

This document details the proposed tabular and graphical presentations of data collected from long term cell delivered ribozyme gene transfer product (OZ1) follow up studies; OZ1-HV1-101, OZ1-HV1-102 and OZ1-HV1-202. This document also defines the analysis populations and the safety and efficacy endpoints.

This document has been written by INC based on information contained in the study protocols OZ1-HV1-101 amendment 2 dated 23 October 2007, OZ1-HV1-102 amendment 2 dated 23 October 2007, and OZ1-HV1-202 amendment 2 dated 28 August 2007 and OZ1-HV1-202 amendment 4 dated 07 Jun 2017

The production of summary tables, data listings, graphs and statistical analyses will be the responsibility of Biometrics at INC, and will be performed according to INC standard operating procedures (SOPs).

One completed analysis which was reported in 2011 covered data collected from the point of First Patient First Visit (FPFV) in January 2000 until the last subject year 5 follow-up visit (Last Patient Last Visit: LPLV) in February 2011. A separate Statistical Analysis Plan (SAP) was used for this previous analysis (Kendle study 76803). This previous SAP has also been used as a template for this new INC study (1003733).

This SAP had covered an interim analysis in 2016 and will cover a final analysis happened after DBL of study *OZ1-HV1-202*. The interim analysis in 2016 was based on cumulative data collected from the point of First Patient First Visit (FPFV) in January 2000 until the last subject year 10 follow-up visit (Last Patient Last Visit (LPLV) in February 2016. The final analysis expected in 2018 will be based on cumulative data collected from the point of FPFV in January 2000 until the last subject completes the end of study visit by 30-Nov-2017.

The previous Kendle study (76803) database used TrialBase software and the new INC study (1003733) database will use Oracle Clinical software. Data extracts from each database into SAS will be combined to create analysis datasets covering the cumulative data from both databases. The analyses in 2018 covered in this SAP will also be based on clean data.

<Protocol: Janssen OZ1-HV1-101/102/202>

<INC code: 1003733>

<SAP Version: 3.0>

---

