### 8.2. ADVERSE EVENTS

Throughout the long term follow-up, all serious adverse events (SAEs) and non-serious related adverse events (NSRAEs) observed by medical staff, or reported by the patient, will be evaluated by the investigator and noted in the adverse event section of the CRF.

SAEs and NSRAEs will be coded using the current Medical Dictionary for Regulatory Activities (MedDRA). SAEs and NSRAEs will be summarized separately for 101, 102 and 202 and overall by tabulating the frequency of reports for each unique event and by tabulating the number of patients experiencing one or more events. The denominator used for the calculation of percentages will be the number of patients in the Safety population for the respective long term follow-ups. SAEs and NSRAEs will be summarized by MedDRA system order class and preferred term. Separate data listings of all information relating to patient death, SAEs and NSRAEs will be provided.

SAEs are defined as events that have a seriousness category of death, life threatening, initial or prolonged hospitalization, disability, congenital anomaly or other medically important condition such as predominant integration site, positive RCR, malignancy or abnormal pregnancy outcome (*ie* recorded seriousness category of 1, 2, 3, 4, 5 or 6). AEs recorded as non-serious (7) will be defined as non-serious and will only be recorded if they are considered related to the gene transfer product. A related AE is defined as any

<Protocol: Janssen OZ1-HV1-101/102/202>

<INC code: 1003733>

<SAP Version: 3.0>

AE whose relationship to the gene transfer product is recorded as possible, probable or very likely (coded on CRF as 3, 4, or 5). Severe AEs are defined as any AE recorded in the 'severe' category (coded on CRF as 3). AEs leading to death are defined as any AE in the seriousness category of 'death' (coded on CRF as 1) and/or an outcome category of 'fatal' (coded on CRF as 5). NSRAEs are defined as adverse events (AEs) whose seriousness category is recorded as non-serious but are considered to have a possible, probable or very likely relationship to the gene transfer product.

If the severity or relationship of an SAE/AE is missing a worst case scenario will be assumed (*ie* the AE will be set to severe or very likely, respectively).

The following AE summary tables will be presented 101, 102, 202 and overall.

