### **8.2.5. Correlation between Frequency of SAEs and NSRAE and Time on Study**

Correlation between OZ1 & LNL6 DNA-PCR (%) and the frequency of SAEs and NSRAEs will be assessed using PROC CORR in SAS. The number of patients on study and experiencing at least one SAE at the timepoints 2.5, 3, 3.5, 4, 4.5, 5, > 5 to ≤ 10 and > 10

<Protocol: Janssen OZ1-HV1-101/102/202>

<INC code: 1003733>

<SAP Version: 3.0>

---

years post infusion will be presented. In addition Spearman's rank correlation co-efficient and its associated p-value overall timepoints will be presented. Similar presentations will be made for patients experiencing at least one NSRAEs.

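### The SAP counts non-serious related adverse events (NSRAEs) over all follow-up since January 2000, although the 202 protocol did not require their recording at first and the SAP states neither a start date nor any back-capture

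*SAP*

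**What the plan says.** SAP 8.2 describes collection as uniform: "Throughout the long term follow-up, all serious adverse events (SAEs) and non-serious related adverse events (NSRAEs) observed by medical staff" are evaluated and entered in the CRF. Percentages use the Safety population of each study as denominator. SAP 1.1 sets the window: the final analysis is "based on cumulative data collected from the point of FPFV in January 2000" up to end-of-study visits by 30 November 2017.

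SAP 8.2.5 presents patients with at least one SAE at 2.5, 3, 3.5, 4, 4.5 and 5 years, at >5 to ≤10 years and at >10 years, with a Spearman coefficient and p-value. For NSRAEs it adds: "Similar presentations will be made for patients experiencing at least one NSRAEs". Its heading and the Table 14.3.5 shell name time on study as the correlate. Its body names DNA-PCR marking (%).

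Protocol 10.2 now carries the rule "Non-serious adverse events must be recorded using medical terminology in the source document and in the case report form", limited to events with a possible, probable or very likely association. Appendix 3 dates that rule to Amendment 2 (28 August 2007) and gives among its reasons to "expand safety reporting requirements to include non-serious, associated adverse events". The original visit lists recorded SAEs. Amendment 1 (23 June 2006) changed them to AEs, but its text for section 9.2 still spoke only of SAEs ("Serious Adverse Event data will be assigned a body system and preferred term using the current MedDRA coding dictionary"), and section 10.2 likewise stayed SAE-only.

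SAP 3.1 acknowledges that data came in under earlier protocol versions and limits the analysis to Table 1 data held on one standardized CRF.

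**The concern.** A patient followed before NSRAEs had to be recorded contributes to the denominator as if observed and event-free. Two biases follow if the gap was not filled later. Early timepoints show too few NSRAEs relative to late ones, so a constant true rate can look like a rise with time since infusion. The overall NSRAE percentages in Tables 14.3.1 and 14.3.3 are also too low, and more so for patients infused earlier.

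The direction matters because the study exists to detect delayed events. An apparent late rise in product-related events could be a recording artefact, and nothing in the SAP lets a reader tell the two apart.

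**Working it through.** The plan states no figure to reproduce, so the check places each timepoint bin on the calendar.

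**Inputs**
- Possible start dates S: 23 June 2006 (2006.47) and 28 August 2007 (2007.65), from Protocol Appendix 3. SAP 1.1 dates amendment 2 of studies 101 and 102 to 23 October 2007 (2007.81). Their AE rules are not in the documents.
- Study 102: "Patients were recruited over the period February 1998 to January 2000" (Appendix 3, Phase I CD34+ study). Recruitment is taken as infusion. The same text has 8 patients in long term follow-up.
- Study 202: last infusion about 13 February 2006 (2006.12), from the last Year 10 date of 13 February 2016 (SAP 6.1) less 10 years. First infusion is not stated, so the start of 2002, 2003 or 2004 is assumed. 37 patients (half of the 74 in Protocol 1.1), evenly spaced, no attrition.
- End of follow-up: 30 November 2017.

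**Formula.** For a bin from a to b years and infusion date t, coverage = Σ max(0, min(t+b, end) − max(t+a, S)) / Σ max(0, min(t+b, end) − (t+a)), summed over patients. The 2.5-year bin runs from 2 to 2.5 years, and so on.

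**Study 102.** The first 2.5-year visit falls at February 1998 + 2.5 years = August 2000. The last Year 5 visit falls at January 2000 + 5 years = January 2005. Both precede June 2006, so coverage of years 2.5 to 5 is 0% under either 202 amendment date. On 23 October 2007 these patients were 7.8 to 9.7 years post infusion. The covered part of the >5 to ≤10 bin is therefore 0.3 to 2.2 of 5 years, about 25% on average. The >10 bin is 100% covered.

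**Study 202**

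| First infusion (assumed) | 2.5-year bin, from Amendment 2 | 2.5-year bin, from Amendment 1 | Year 5 bin, from Amendment 2 | Patient-years before Amendment 2 |
|---|---|---|---|---|
| 2002 | 18% | 46% | 77% | 14% |
| 2003 | 24% | 61% | 99% | 10% |
| 2004 | 34% | 88% | 100% | 6% |

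Coverage after year 5 is 99-100% in every row. Hand check of the first cell: half of the 2 to 2.5 year window is covered when t + 2.25 = 2007.65, so t = 2005.40. The share infused later is (2006.12 − 2005.40)/(2006.12 − 2002.00) = 0.72/4.12 = 17.5%.

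For 102 and 202 pooled, which is a column of Table 14.3.5, 14-20% of patient-years precede Amendment 2.

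**Effect on a time correlation.** Simulation with a constant true rate (assumed 0.05 or 0.10 per patient-year), first 202 infusion assumed 2003, and bin order correlated with at least one event; ranges cover 202 alone and 102 plus 202:

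| Bins | Complete recording | Recording only from Amendment 2 |
|---|---|---|
| Equal 6-month bins | mean rho about 0.00; p<0.05 in about 4-5% of runs | mean rho +0.03 to +0.05; p<0.05 in 11-31% |
| The SAP's bins | mean rho +0.21 to +0.29 | mean rho +0.25 to +0.34 |

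The first row isolates the recording change. The second shows that unequal bin width alone produces a larger rise.

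**The case against.** **The standardized CRF may have cured the problem.** SAP 3.1 shows the authors knew that protocol versions differed. Events in clinic notes could have been abstracted onto that form later. This stands as a possibility: the documents neither state nor exclude back-capture. But only complete back-capture removes the bias, and the SAP does not claim it.

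**The start date is not settled.** A reader might infer that NSRAEs were recorded only from August 2007. The Amendment 1 visit lists already asked for AEs in June 2006, so that reading is too firm, and neither date is established for 101 or 102. This stands, and it is why both dates are shown for 202.

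**Time may not be the correlate.** The body of SAP 8.2.5 names marking, and the Table 14.3.5 shell prints rho separately at each visit, where time is nearly fixed. A rise in the NSRAE rhos therefore cannot be called certain. The counts by timepoint and the Safety-population percentages are affected whichever correlate is meant.

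**Bin width is the larger artefact.** Six-month bins are followed by a 5-year bin and an open one, and this also inflates late SAE counts. That stands as a separate defect; incomplete recording adds to it.

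**An amendment log describes superseded text.** True, and no conflict with current text is alleged. The log is used only to date what sites were asked to record in a period that the SAP pools.

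**Conclusion.** The point holds in conditional form. The SAP assumes uniform NSRAE capture over a period in which the 202 requirement changed, and it gives no start date, at-risk rule or caveat. Without complete back-capture, NSRAE-by-time results are biased upward and overall NSRAE percentages downward.

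The effect would be greatest for the early timepoints of 102, provided its rules followed the 202 timetable. For 202 it is largely confined to the years before year 5. At a constant rate with no earlier capture, the expected 202 NSRAE count would fall short by 6-14% if recording began with Amendment 2. Placebo patients, who are in the Safety population until withdrawn, and study 101 are not in these figures.

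Two stronger readings are tempting. One is that NSRAEs must rise with time by construction. That is not supported: back-capture is unknown, the correlate is in dispute, and in equal bins a true decline of about 10% a year would cancel the effect. The other is a single inflation factor, such as about 5-fold from the 2.5-year bin to beyond year 10. For 102 and 202 pooled, coverage of the first bin from Amendment 2 is 15%, 19% or 28% for first infusion in 2002, 2003 or 2004, giving ratios of 6.7, 5.3 or 3.6. From Amendment 1 it is 37/45 of 46%, 61% or 88%, that is 38%, 50% or 72%, giving 2.6, 2.0 or 1.4. The documents do not give the date needed to choose among these.

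Protocol 9 makes the analysis primarily descriptive, which limits the harm. The correction is still worthwhile because the bias points toward delayed toxicity.

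**What to change.** - In SAP 8.2 and 8.2.5, state for each study the date and CRF version from which NSRAEs were captured, and whether earlier events were back-captured.
- If back-capture was complete, say so; no change to the NSRAE analyses is then needed on this account.
- If it was not complete, count NSRAE time at risk and denominators in Tables 14.3.1, 14.3.3 and 14.3.5 only from that date. Show earlier bins as *not collected* rather than zero. Drop the NSRAE-by-time correlation or restrict it to the covered period.
- Reconcile the heading of 8.2.5 and Table 14.3.5 (time on study) with the body of 8.2.5 (marking %).
- Deal with the unequal bins separately, for SAEs as well as NSRAEs, for example with rates per patient-year.

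The cost is SAP wording and one date filter in the programs. The downside is that fewer patients and less time contribute to the NSRAE summaries.
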